Research question and objectives	
The aim of this study it to characterise individuals treated with Azathioprine.
 
The specific study objectives are:
 
 1. Characterisation of patients newly treated with Azathioprine by sex and age at first prescription, overall and per indication 2. Characterisation of patients newly treated with Azathioprine by indication: 
 a. Organ transplantation b. Severe rheumatoid arthritis or chronic polyarthritis c. Inflammatory bowel disease d. Autoimmune hepatitis e. Systemic lupus erythematosus f. Dermatomyositis g. Polyarteritis nodosa h. Pemphigus vulgaris and bullous pemphigoid i. Behcet's disease j. Refractory autoimmune haemolytic anaemia k. Refractory idiopathic thrombocytopenic purpura l. Polymyositis m. Pyoderma gangrenosum n. Multiple sclerosis o. Myasthenia gravis p. None of the above/missing 3. Large-scale characterisation overall and per indication of drugs and conditions within one year prior to the index date (-365 to -1 day to the index date) and on the index date will be assessed. 4. Characterisation of patients newly treated with Azathioprine in terms of treatment duration, overall and for each indication
Country(ies) of study	
This study will include 5 databases, representing 4 countries in Europe:
 
 • Germany: IQVIA DA Germany • United Kingdom: CPRD GOLD • Netherlands: IPCI • Spain: IMASIS and SIDIAP
Author	
[name] ([contact])
 
[name] ([contact])

	D2.2.3 - Study Protocol for P3-C1-014	
	Author(s): [name], [name]	Version: V4.0
	Dissemination level: Public	

LIST OF ABBREVIATIONS

Acronyms/term	Description
CDM	Common Data Model
CC	Coordinating centre
CPRD	Clinical Practice Research Datalink
DA	Disease Analyzer
DARWIN EU®	Data Analysis and Real-World Interrogation Network
DRE	Digital Research Environment
DQD	Data Quality Dashboard
DUS	Drug Utilisation Study
EHR	Electronic Health Records
ED	Emergency department
EMA	European Medicines Agency
ENCePP	European Network of Centres for Pharmacoepidemiology and Pharmacovigilance
EU	European Union
GDPR	General Data Protection Regulation
ICD	International Classification of Diseases
ID	Index date
IMASIS	Institut Municipal Assistència Sanitària Information System
IP	Inpatient
IPCI	Integrated Primary Care Information
LPD	Longitudinal Patient Database
MA	Marketing Authorisation
MS	Multiple Sclerosis
OHDSI	Observational Health Data Sciences and Informatics
OMOP	Observational Medical Outcomes Partnership
OP	Outpatient
PRAC	Pharmacovigilance Risk Assessment Committee
PSMAR	Consorti Mar Parc de Salut Barcelona
SD	Standard deviation
SIDIAP	The Information System for Research in Primary Care
SLE	Systemic Lupus Erythematosus
SNOMED	Systematized Nomenclature of Medicine
WHO	World Health Organisation

	D2.2.3 - Study Protocol for P3-C1-014	
	Author(s): [name], [name]	Version: V4.0
	Dissemination level: Public	

1. TITLE

DARWIN EU® - Azathioprine – user characteristics

3. ABSTRACT

Title

DARWIN EU® – Azathioprine – user characteristics

Rationale and background

Azathioprine is a purine analogue and prodrug of mercaptopurine that is used as an immunosuppressive medication alone or in combination with other immunosuppressive therapy to prevent rejection following organ transplantation and to treat certain autoimmune diseases, where it is considered a steroid-sparing agent. The Pharmacovigilance Risk Assessment Committee (PRAC) recently discussed a signal procedure regarding the association between treatment with azathioprine and non-cirrhotic portal hypertension/porto-sinusoidal vascular disease (PSVD).

Through this study we aim to characterize patients newly treated with azathioprine, to contextualise the signal assessment.

Research question and objectives

This is a study in incident users of azathioprine aiming to characterise new users of azathioprine with respect to indications for treatment, age at treatment initiation, and sex, and to summarise the treatment durations with azathioprine for all indications combined, and for each individual treatment indication.

Study specific objectives are as following:

1. Characterisation of patients newly treated with Azathioprine by sex and age at first prescription, overall and per indication
2. Identify potential indications for azathioprine, and the percentage of azathioprine-treated patients for each pre-defined approved indication:
 - a) Organ transplantation
 - b) Severe rheumatoid arthritis or chronic polyarthritis
 - c) Inflammatory bowel disease
 - d) Autoimmune hepatitis
 - e) Systemic lupus erythematosus
 - f) Dermatomyositis
 - g) Polyarteritis nodosa
 - h) Pemphigus vulgaris and bullous pemphigoid
 - i) Behçet's disease
 - j) Refractory autoimmune haemolytic anaemia
 - k) Refractory idiopathic thrombocytopenic purpura
 - l) Polymyositis
 - m) Pyoderma gangrenosum
 - n) Multiple sclerosis
 - o) Myasthenia gravis.
 - p) None of the above/missing
3. Large-scale characterisation overall and per indication of drugs and conditions within one year prior to the index date (-365 to -1 day to the index date) and on the index date will be assessed.
4. Estimate and summarise duration of treatment with azathioprine, overall, and stratified per indication.

	D2.2.3 - Study Protocol for P3-C1-014	
	Author(s): [name], [name]	Version: V4.0
	Dissemination level: Public	

Methods

Study design

Patient-level drug utilisation study

Study period

01/01/2000 – 31/12/2023

Population

For this study we have one cohort, namely:

- Population of individuals newly treated with Azathioprine

Data source

1. Clinical Practice Research Datalink (CPRD) GOLD, United Kingdom
2. Integrated Primary Care Information (IPCI), Netherlands
3. IQVIA Disease Analyzer Germany (IQVIA DA Germany), Germany
4. Institut Municipal Assistència Sanitària Information System (IMASIS), Spain
5. The Information System for Research in Primary Care (SIDIAP), Spain

Sample size

Based on a preliminary feasibility assessment, the expected person counts for Azathioprine were 900 for IMASIS, 6,000 for IPCI, 23,700 for IQVIA DA Germany, 24,500 for SIDIAP and 52,100 for CPRD GOLD.

Exposure of interest

Azathioprine use.

Outcomes of interest

- Characteristics (sex and age)
- Indication
 - Organ transplantation
 - Severe rheumatoid arthritis or chronic polyarthritis
 - Inflammatory bowel diseases
 - Autoimmune hepatitis
 - Systemic lupus erythematosus
 - Dermatomyositis
 - Polyarteritis nodosa
 - Pemphigus vulgaris and bullous pemphigoid
 - Behcet's disease
 - Refractory autoimmune haemolytic anaemia
 - Refractory idiopathic thrombocytopenic purpura
 - Polymyositis
 - Pyoderma gangrenosum

	D2.2.3 - Study Protocol for P3-C1-014	
	Author(s): [name], [name]	Version: V4.0
		Dissemination level: Public

- Multiple sclerosis
- Myasthenia gravis
- None of the above/missing
- Large-scale characterisation: overall and per indication of drugs and conditions within one year prior to the index date (-365 to -1 day to the index date) and on the index date
- Treatment duration, overall and by indication

Statistical analysis

Characterisation of individuals newly initiating treatment with Azathioprine will be done using the *CohortCharacteristics* and *CohortDiagnostics* R packages. For the second and third objective, we will use the *DrugUtilisation* package to characterise Azathioprine use including counts (%) for each indication, and treatment duration.

	D2.2.3 - Study Protocol for P3-C1-014	
	Author(s): [name], [name]	Version: V4.0
		Dissemination level: Public

4. AMENDMENTS AND UPDATES

None.

5. MILESTONES

Study deliverables	Timelines
Draft Study Protocol	23/08/2024
Final Study Protocol	25/09/2024
Creation of Analytical code	August/September 2024
Execution of Analytical Code on the data	September/October 2024
Draft Study Report	15/10/2024
Final Study Report	15/11/2024

6. RATIONALE AND BACKGROUND

Azathioprine is a purine analogue and prodrug of mercaptopurine that is used as an immunosuppressive medication alone or in combination with other immunosuppressive therapy to prevent rejection following organ transplantation and to treat certain autoimmune diseases, where it is considered a steroid-sparing agent. Examples of autoimmune diseases that could be treated with azathioprine are rheumatoid arthritis, inflammatory bowel disease, systemic lupus erythematosus (SLE), polymyositis, dermatomyositis, multiple sclerosis (MS) and myasthenia gravis(1-7).

Azathioprine is associated with minor usually transient and asymptomatic elevations of aminotransferase levels and with rare instances of acute cholestatic liver injury and with long-term use, portal hypertension may occur(8, 9).

A signal procedure regarding a potential association between azathioprine and non-cirrhotic portal hypertension/portosinusoidal vascular disease (PSVD) - which is a rare disorder characterised by signs of portal hypertension in the absence of an identifiable aetiology, such as cirrhosis - is needed. A liver biopsy is mandatory for the diagnosis of PSVD.(10) Specific histologic signs include obliterative portal venopathy, nodular regenerative hyperplasia and incomplete septal fibrosis (10).

This study is intended to support the signal evaluation by providing information about the use of azathioprine, including the most frequent indications, the age- and sex distribution at initiation of treatment, and the treatment duration for all indications combined, and for each indication separately.

	D2.2.3 - Study Protocol for P3-C1-014	
	Author(s): [name], [name]	Version: V4.0
	Dissemination level: Public	

7. RESEARCH QUESTION AND OBJECTIVES

The aim of this study is to characterise individuals treated with Azathioprine.

The specific study objectives are:

1. Characterise azathioprine initiators by sex and age at first prescription, overall and per indication
2. Identify potential indications for azathioprine, and the percentage of azathioprine-treated patients for each pre-defined approved indication:
 - a) Organ transplantation
 - b) Severe rheumatoid arthritis or chronic polyarthritis
 - c) Inflammatory bowel disease
 - d) Autoimmune hepatitis
 - e) Systemic lupus erythematosus
 - f) Dermatomyositis
 - g) Polyarteritis nodosa
 - h) Pemphigus vulgaris and bullous pemphigoid
 - i) Behçet's disease
 - j) Refractory autoimmune haemolytic anaemia
 - k) Refractory idiopathic thrombocytopenic purpura
 - l) Polymyositis
 - m) Pyoderma gangrenosum
 - n) Multiple sclerosis
 - o) Myasthenia gravis
 - p) None of the above/missing
3. Large-scale characterisation overall and per indication of drugs and conditions within one year prior to the index date (-365 to -1 day to the index date) and on the index date will be assessed.
4. Estimate and summarise duration of treatment with azathioprine, overall, and stratified per indication

Description of the proposed objectives are described in ([Table 1](#)).

Table 1. Primary and secondary research questions and objective.

A. Primary research question and objective.

Objective 1,2,3 and 4:	To characterise individuals newly treated with Azathioprine by age and sex. In addition, new users of Azathioprine will be characterised in terms of indication and treatment of use. Characterisation will be done in terms of demographics, indication, treatment duration and prior drug use and comorbidities
Hypothesis:	N/A
Population (mention key inclusion-exclusion criteria):	All patients present in the databases with at least 365 days of prior history and newly treated with Azathioprine
Exposure:	Exposure to Azathioprine

	D2.2.3 - Study Protocol for P3-C1-014	
	Author(s): [name], [name]	Version: V4.0
	Dissemination level: Public	

Comparator:	N/A
Outcome:	N/A
Time (when follow up begins and ends):	
Study period will be from 1st January 2000 to 31st December 2023. Within this study period, we will identify individuals newly treated with azathioprine.
 
To generate information on duration of use, follow-up will be from the first date of azathioprine during the study period until 1) censoring or loss to follow-up, 2) end of data availability, or 3) the end date of exposure (whichever occurs first).

Setting:	Primary care data (CPRD GOLD, IPCI, IQVIA DA Germany and SIDIAP) and outpatient secondary care (IQVIA DA Germany)
Main measure of effect:	Counts

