8.2 Study setting and data sources

This study will use routinely collected health data from 5 databases in the DARWIN EU[®] network of data partners from 4 European countries. All databases were previously mapped to the OMOP CDM.

Data sources

1. Clinical Practice Research Datalink (CPRD) GOLD, United Kingdom
2. Integrated Primary Care Information (IPCI), Netherlands
3. IQVIA Disease Analyzer Germany (IQVIA DA Germany), Germany
4. Institut Municipal Assistència Sanitària Information System (IMASIS), Spain
5. The Information System for Research in Primary Care (SIDIAP), Spain

These databases fulfil the criteria required for patient-level drug utilisation, and characterisation allowing for large-scale characterisation while covering different regions of Europe. The selection of databases was based on the availability of data on the selected drugs of interest, the conditions of interest, and other

	D2.2.3 - Study Protocol for P3-C1-014	
	Author(s): [name], [name]	Version: V4.0
		Dissemination level: Public

variables needed to perform the described analyses. As information needs to be provided in a timeline manner, data partners not requiring IRB approval or DPs with fast IRB review time (for instance because of basket protocol approval) have been selected. Detailed information on the selected data sources is described in [Table 3](#).

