Netherlands	IPCI	Adequate number of patients exposed to Azathioprine, availability of medical history for cohort characterisation. Able to perform study and produce results before mid-October deadline.	Primary Care	EHR	1.39m	15,700	30/04/2024
Spain	SIDIAP	Adequate number of patients exposed to Azathioprine, availability of medical history for cohort characterisation.	Primary care	EHR	5.8m	29,200	30/06/2023
Germany	IQVIA DA Germany	Adequate number of patients exposed to Azathioprine, availability of medical history for	Primary care and outpatient	EHR	43m	80,400	30/09/2023

	D2.2.3 - Study Protocol for P3-C1-014	
	Author(s): [name], [name]	Version: V4.0
	Dissemination level: Public	

Country	Name of Database	Justification for Inclusion	Health Care setting (e.g. primary care, specialist care, hospital care)	Type of Data (EHR, claims, registries)	Number of active subjects	Feasibility count of exposure (Azathioprine)*	Data lock for the last update
		cohort characterisation. Able to perform study and produce results before mid-October deadline.	secondary care				
Spain	IMASIS	Adequate number of patients exposed to Azathioprine, availability of medical history for cohort characterisation. Able to perform study and produce results before mid-October deadline.	Inpatient hospital care and secondary outpatient care	EHR	1.1m	2,100	10/02/2024

Version: V2.0 Dissemination level: Public	D2.2.3 - Study Protocol for P3-C1-014	
	Author(s): [name], [name]	Version: V4.0
		Dissemination level: Public

Clinical Practice Research Datalink GOLD, United Kingdom (University of Oxford)

The Clinical Practice Research Datalink (CPRD) GOLD is a database of anonymised electronic health records (EHR) from General Practitioner (GP) clinics in the UK that use the Vision® software system for their management.(11) The source population encompasses 98% of the UK, registered with GPs responsible for non-emergency care and referrals. Participating GPs provide CPRD EHR for all registered patients who did not specifically request to opt out of data sharing. Covering 4.6% of the current UK population, GOLD includes 4.9% of contributing GP practices, providing comprehensive information within its defined source population. GOLD contains data from all four UK constituent countries and the current regional distribution of its GP practices is 5.7% in England, 55.6% in Scotland, 28.4% in Wales, and 10.2% in Northern Ireland (May 2022).

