The Institut Municipal Assistència Sanitària Information System (IMASIS) is the Electronic Health Record (EHR) system of Parc de Salut Mar Barcelona (PSMar) which is a complete healthcare services organisation. Currently, this information system includes and shares the clinical information of two general hospitals (Hospital del Mar and Hospital de l’Esperança), one mental health care centre (Centre [name]) and one social-healthcare centre (Centre Fòrum) including emergency room settings, that are offering specific and different services in the Barcelona city area (Spain). At present, IMASIS includes clinical information from around 1 million patients with at least one diagnosis and who have used the services of this healthcare system since 1990 and from different settings such as admissions, outpatients, emergency room and major ambulatory surgery. The diagnoses are coded using The International Classification of Diseases ICD-9-CM and ICD-10-CM. The average follow-up period per patient in years is 6.37 (SD±6.82). IMASIS-2 is

	D2.2.3 - Study Protocol for P3-C1-014	
	Author(s): [name], [name]	Version: V4.0
		Dissemination level: Public

the anonymised relational database of IMASIS which is used for mapping to OMOP including additional sources of information such as the Tumours Registry.

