8.5 Study population with inclusion and exclusion criteria

The study population will include all individuals observed in one of the participating data sources during the study period (1st January 2000 to 31st December 2023) and having at least 1 year of database history.

Patients will be excluded if the start date in the database falls within 365 days prior to the index date, as sufficient data availability is required.

The operational definitions of the inclusion and exclusion criteria are presented by means of **Table 5** and **Table 6** , respectively.

	D2.2.3 - Study Protocol for P3-C1-014	
	Author(s): [name], [name]	Version: V4.0
	Dissemination level: Public	

Table 5. Operational definitions of inclusion criteria.

Criterion	Details	Order of application	Assessment window	Care Settings ¹	Code Type	Diagnosis position ²	Applied to study populations:
Prior database history	Study participants will be required to have 365 days of prior history observed before the index date	Prior	[-365,-1]	OP	N/A	N/A	All individuals within selected databases
Observation period in the database during the period	All individuals present in the 2000-2023 (or the latest date available)	after	N/A	OP	N/A	N/A	All individuals within selected databases
User of Azathioprine (exposure)	Prescription record of azathioprine	after	Study period	OP	RxNorm	N/A	All individuals within selected databases

¹ IP = inpatient, OP = outpatient, ED = emergency department, OT = other, n/a = not applicable

² Specify whether a diagnosis code is required to be in the primary position (main reason for encounter)

	D2.2.3 - Study Protocol for P3-C1-014	
	Author(s): [name], [name]	Version: V4.0
	Dissemination level: Public	

Table 6. Operational definitions of exclusion criteria.

Criterion	Details	Order of application	Assessment window	Care Settings ¹	Code Type	Diagnosis position ²	Applied to study populations:	Measurement characteristics/validation	Source for algorithm
N/A	N/A	N/A	N/A	N/A	N/A	N/A	N/A	N/A	N/A

¹ IP = inpatient, OP = outpatient, ED = emergency department, OT = other, n/a = not applicable

² Specify whether a diagnosis code is required to be in the primary position (main reason for encounter)

	D2.2.3 - Study Protocol for P3-C1-014	
	Author(s): [name], [name]	Version: V4.0
		Dissemination level: Public

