8.6.1 Exposure/s

Azathioprine exposure consists of a prescription record of azathioprine (for systemic use thus oral or parenteral use). The operational definition of exposure is described by means of **Table 7**.

	D2.2.3 - Study Protocol for P3-C1-014	
	Author(s): [name], [name]	Version: V4.0
	Dissemination level: Public	

Table 7. Operational definitions of exposure.

Exposure group name(s)	Details	Washout window	Assessment Window	Care Setting ¹	Code Type	Diagnosis position ²	Applied to study populations	Incident with respect to...	Measurement characteristic s/ validation	Source of algorithm
Azathioprine	Preliminary code lists provided in Appendix I	[-inf,-1], for incident use only	Anytime post start of the study date	OP	RxNorm	N/A	All eligible individuals in the database	Azathioprine use	N/A	N/A
Azathioprine + indication of use	Preliminary code lists provided in Appendix I	n/a = not applicable	Indication of use in - 90/+30 days of index date	OP	SNOMED codes to assess indication of use	Yes (indication of use)	All incident users of azathioprine	Azathioprine use	N/A	N/A

¹ IP = inpatient, OP = outpatient, ED = emergency department, OT = other, n/a = not applicable

² Specify whether a diagnosis code is required to be in the primary position (main reason for encounter)

	D2.2.3 - Study Protocol for P3-C1-014	
	Author(s): [name], [name]	Version: V4.0
	Dissemination level: Public	

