 - Treatment duration overall and per indication, will be assessed from the index date until date of: 1) censoring or loss to follow-up, 2) end of data availability, or 3) the end date of exposure (whichever occurs first). Furthermore, to provide more context, also the proportion (%) of patients with a duration that fall within a prespecified treatment duration group will be calculated and provided, both for the overall treatment duration as per indication. The prespecified treatment duration groups will be: <12 months, 12-24 months, 2-3 years, 3-4 years, 4-5 years, 5-10 years and ≥10 years.

	D2.2.3 - Study Protocol for P3-C1-014	
	Author(s): [name], [name]	Version: V4.0
	Dissemination level: Public	

Table 9. Operational definitions of covariates.

Characteristic	Details	Type of variable	Assessment window	Care Settings ¹	Code Type	Diagnosis Position ²	Applied to study populations	Measurement characteristics / validation	Source for algorithm
Demographics	Age and sex at index date	Numeric, continuous, binary	All history	OP	N/A	N/A	Incident azathioprine users	N/A	N/A
Indications	Prespecified indications of interest - 90/+30 days of the index date	Count, binary	[-90, +30]	OP	SNOMED	N/A	Incident azathioprine users	N/A	N/A
Medication use, comorbidities	All history prior to the index date (large-scale characterisation)	Count, binary	[-365, -1] and [0,0]	OP	SNOMED, RxNorm	N/A	Incident Azathioprine users	N/A	N/A
Treatment duration	Duration of treatment with Azathioprine for the: 
 - new users of azathioprine use - New users of azathioprine per indication 	Numeric, continuous	[0, end of exposure]	OP	N/A	N/A	Incident azathioprine users	N/A	N/A

¹ IP = inpatient, OP = outpatient, ED = emergency department, OT = other, n/a = not applicable

² Specify whether a diagnosis code is required to be in the primary position (main reason for encounter)

	D2.2.3 - Study Protocol for P3-C1-014	
	Author(s): [name], [name]	Version: V4.0
		Dissemination level: Public

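### Table 1 leaves out IMASIS and Tables 4, 5, 7 and 9 admit outpatient records only, although IMASIS enters the study with inpatient and emergency data

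*Protocol*

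**What the plan says.** Section 8.2 announces five databases ("This study will use routinely collected health data from 5 databases in the DARWIN EU") and lists "Institut Municipal Assistència Sanitària Information System (IMASIS), Spain" among them. Table 3 gives the care setting of IMASIS as "Inpatient hospital care and secondary outpatient care". The database description in the same section says its records come from "different settings such as admissions, outpatients, emergency room and major ambulatory surgery". No other row of Table 3 lists inpatient care.

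In section 7, the Setting row of Table 1 reads "Primary care data (CPRD GOLD, IPCI, IQVIA DA Germany and SIDIAP) and outpatient secondary care (IQVIA DA Germany"). IMASIS is not named and no inpatient care is mentioned.

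The care-setting column is OP for the index date (Table 4), for all three inclusion criteria (Table 5, including "Prescription record of azathioprine"), for both exposure definitions (Table 7) and for all four covariate groups (Table 9, including "Prespecified indications of interest - 90/+30 days of the index date"). The table footnotes define inpatient, outpatient and emergency department as separate codes.

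Table 7 also enters "Yes (indication of use") under diagnosis position. Its footnote explains that this column says whether a code must be in the primary position. Table 9 has N/A for the same indication variable.

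**The concern.** Tables 4, 5, 7 and 9 are the operational definitions, and section 8.6.1 sends the reader to Table 7 for how exposure is defined. For the four other databases the OP entry fits the settings in Table 3. For IMASIS it admits only part of the data that Table 3 describes, and nothing exempts IMASIS from it.

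Two of the study's main results depend on this. One is new-user status, because a hospital start that is not seen can neither set the index date nor exclude a later outpatient prescription from being the first. The other is indication, because a diagnosis recorded only during an admission would not be found in the window around the index date. Treatment duration follows the index date: if the first era starts late, its early part is lost.

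**Working it through.** The plan states no figure that could be reproduced here. The check sets the passages side by side and counts the entries.

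**1. Databases named.** Section 8.2 and Table 3 name 5. The Setting row of Table 1 names 4: CPRD GOLD, IPCI, IQVIA DA Germany and SIDIAP. The missing one is IMASIS.

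**2. Care-setting cells.**

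| Table | Populated rows | OP | IP or ED |
|---|---|---|---|
| 4 (index date) | 1 | 1 | 0 |
| 5 (inclusion) | 3 | 3 | 0 |
| 7 (exposure) | 2 | 2 | 0 |
| 9 (covariates) | 4 | 4 | 0 |
| Total | 10 | 10 | 0 |

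Tables 6 and 8 are N/A throughout and restrict nothing. Because the footnotes list IP, OP and ED separately, OP cannot be read as covering admissions or emergency visits.

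**3. Narrative definitions.** Table 1 takes as its population all patients in the databases who meet the history and new-use conditions. Section 8.5 takes everyone observed in a participating source with a year of history. Section 8.6.1 defines exposure as any systemic azathioprine prescription record, oral or parenteral. Section 8.8.1 takes duration from the drug exposure table of the common data model. None of these mentions a care setting.

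**4. Literal application to IMASIS.**
- Index date (Table 4) and washout (Table 7, any time before): inpatient azathioprine records are ignored in both. A patient started in hospital and continued in the outpatient clinic gets the first outpatient record as index date and passes the washout as a new user. A patient with inpatient records only does not enter.
- The -365 to -1 day and -90 to +30 day windows move with the index date.
- Indications (Table 9): a code recorded only during an admission is not counted. If no outpatient code falls in the window, the patient goes to the none/missing category.

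**5. Size.** Section 8.7 expects 900 + 6,000 + 23,700 + 24,500 + 52,100 = 107,200 persons. IMASIS is 900 / 107,200 = 0.84% of them. Sections 8.8 and 8.9 report each database separately without meta-analysis, so the other four sets of results are untouched and the IMASIS results carry the whole effect. With an unknown share s of IMASIS patients affected, the number is 900 × s. The documents give no value for s, so the range runs from 900 × 0 = 0 to 900 × 1 = 900.

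**6. Diagnosis position.** Section 8.6.3 identifies indications by the presence of disease codes, with no position requirement, and Table 9 agrees. Only the Table 7 cell differs.

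**The case against.** The strongest reply is that the OP column is a template descriptor that was not updated when IMASIS was included. The column also says OP for age and sex, for treatment duration and for being observed in the database, where a visit filter is hard to interpret. The narrative definitions have no filter, and neither do the concept lists in Appendix I, so the code may well use all IMASIS records. This stands: the harm is conditional on literal application. It does not remove the contradiction. Table 1 points the same way as the OP cells, so a reader cannot tell an oversight from an outpatient-only intention. If the code does use all records, the protocol misdescribes the IMASIS analysis.

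Four stronger readings are tempting, and the documents do not support them.
- A reader might infer that OP defeats the purpose of including IMASIS. Table 3 justifies IMASIS by the number exposed, the available medical history and timely delivery. Section 8.2 adds data availability, regional coverage and fast ethics review. Inpatient coverage is never given as a reason, and the secondary outpatient records of IMASIS would survive the restriction.
- A reader might assume an inpatient share and quote a number of patients lost. No such share is given.
- A reader might conclude that transplant patients necessarily end up without an indication. The concept set in Appendix I includes transplant follow-up and transplant-related disorders, which an outpatient clinic can record.
- A reader might take the Table 7 position cell to exclude secondary-position diagnoses. Section 8.6.3 and Table 9 largely settle that it does not. The cell is muddled rather than a rule.

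**Conclusion.** The protocol contradicts itself on which IMASIS records count. Table 1 and ten of ten populated care-setting cells exclude inpatient and emergency records. Section 8.2 and Table 3 bring IMASIS in with them, and the narrative definitions do not restrict. The inconsistency is certain. The consequence (late index dates, prevalent users counted as new, missed patients, some indications moved to none/missing) follows only if the OP entries are applied as written.

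The effect is limited to the IMASIS results: 0.84% of all expected persons, but 100% of that database's separately reported tables. The number affected lies between 0 and 900 and cannot be narrowed from the documents. That range assumes that the 900 persons in section 8.7 were counted over all IMASIS settings, which the protocol does not state. Correction before the code is run is worthwhile, because new-user status and indication are what the study reports and the repair is almost free.

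**What to change.** - **Table 1, Setting row:** add IMASIS with inpatient hospital care and secondary outpatient care.
- **Tables 4, 5, 7 and 9, care setting:** keep OP for the other four databases and enter all recorded settings (IP, OP, ED) for IMASIS. This agrees with Table 3 and the unrestricted narrative definitions. If an outpatient-only analysis is intended, say so in sections 8.5 and 8.6, and state in section 11 what it means for new-user status and indications in IMASIS.
- **Table 7, diagnosis position:** change the cell to N/A (any position), in line with Table 9 and section 8.6.3. This is a minor alignment.
- **Check:** confirm that the study code applies the rule that the tables state.

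The cost is a few table edits and one check of the code. No new data are needed.
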